6.3.2 Assessment of Secondary Efficacy Endpoints

Highest tolerated dose and cumulative dose. The highest dose of roasted peanut protein tolerated by the subject, cumulative total dose of roasted peanut protein tolerated by the subject, and the changes in highest tolerated dose and cumulative tolerated dose from initial OFC to the peanut protein arm of the exit DBPCFC will be analyzed as ordinal variables because of the interval nature of the dosing schedule (Chinchilli et al., 2005). The dose schedule for initial OFC and exit DBPCFC is shown below.

Peanut protein challenge dose schedule at initial (SV 1) and exit (SV 10) oral food challenges.

Oral food challenge	Highest tolerated dose of peanut protein (mg)	Cumulative tolerated dose of peanut protein (mg) at initial OFC	Cumulative tolerated dose of peanut protein (mg) at exit DBPCFC
Initial only	5	5	
Initial only	10	15	
Initial and Exit	25	40	25
Initial only	50	90	
Initial and Exit	100	190	125
Exit only	200		325
Exit only	300		625
Initial only	500	690	
Exit only	600		1225
Initial and Exit	1000	1690	2225
Initial only	4000	5690	

Serum markers of sensitization and tolerance to peanut. Changes in serum markers of sensitization and tolerance to peanut from initial dose escalation visit to final study visit will be analyzed as continuous variables.

Food Allergy Quality of Life Questionnaires (FAQQLQ). The Food Allergy Quality of Life Questionnaire – Parent Form (FAQQLQ-PF) will be used for patients aged 0-12 years (DunnGalvin et al., 2008). The Food Allergy Quality of Life Questionnaire –Teenager Form (FAQQLQ-TF) will be used for patients aged 13-17 year (Flokstra-de Blok et al., 2008). For all FAQQLQ surveys, all questions are scored on an ordered scale from 1 (“no impairment”) to 7 (“maximal impairment”) for calculations. Subscale and summary scores are calculated as item mean scores, on the same scale from 1 to 7. Subscale and summary scores, and changes in subscale and summary scores from enrollment/baseline visit to final study visit, will be analyzed as continuous variables. The MID (minimally important difference) for the FAQQLQ is 0.5 (DunnGalvin et al., 2010), and the change in total score will be dichotomized as greater than or equal to 0.5 or less than 0.5 and analyzed as a binary variable. Scoring of the FAQQLQ is detailed in section 9.3.2.

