9.2.2 Derivation of Secondary Efficacy Endpoints

Highest tolerated dose and cumulative dose. The highest tolerated dose at initial OFC will be the largest amount in milligrams to which the question, 'Was *amount* dose tolerated' on the CRF for the initial OFC was marked 'Yes'. The highest tolerated dose at exit DBFCFC will be the largest amount in milligrams to which the question, 'Was *amount* dose tolerated' was marked 'Yes' on the CRF corresponding to the peanut protein arm of the exit DBFCFC. At both the initial OFC and exit DBFCFC, if the lowest dose given was not tolerated, the highest tolerated dose will be zero. The change in highest tolerated dose will be calculated as the difference between the final and initial highest tolerated doses.

The cumulative tolerated dose at initial OFC will be the sum in milligrams of all doses in which the question, 'Was *amount* dose tolerated' on the CRF for the initial OFC was marked 'Yes'. The cumulative tolerated dose at exit DBFCFC will be the sum in milligrams of all doses in which the question, 'Was *amount* dose tolerated' was marked 'Yes' on the CRF corresponding to the peanut protein arm of the DBFCFC. At both the initial OFC and exit DBFCFC, if the lowest dose given was not tolerated, the cumulative tolerated dose will be zero. The change in cumulative tolerated dose will be calculated as the difference between the final and initial highest tolerated doses.

Serum markers of sensitization and tolerance to peanut. The change in each serum marker will be calculated as the difference between the final and initial values.

FAQLQ. Questionnaires will be scored according to scoring sheets downloaded from the FAQLQ website (faqlq.com, accessed November 1, 2021). The change in the summary score and each subscale score from baseline to follow-up FAQLQ will be calculated for each patient. The MID (minimally important difference) for the FAQLQ is 0.5 (DunnGalvin et al., 2010); each change score will be categorized as greater than or equal to the MID (≥ 0.5), or less than the MID (< 0.5). The number and percent of missing items will be assessed for the summary score and each subscale score, and scores will not be calculated if the percent of missing items is greater than 20%, as recommended on the FAQLQ website (http://faqlq.com/?page_id=15). *Item mean scores* will be calculated as the sum of all non-missing item response values divided by the number of non-missing items.

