- Subjects ages 0-12 years. The Food Allergy Quality of Life Questionnaire – Parent Form (FAQLQ-PF) for ages 0-12 years has different scoring sheets for age group 0-3, 4-6, and 7-12; there are 3 subscale scores and a summary score for all age groups (<http://faqlq.com/wp-content/uploads/2011/11/FAQLQ-PF-scoring-sheet-all-age-groups.pdf>). Subscale scores are item mean scores for the specified questions, and the summary score is the mean of the three subscale scores. If one or more subscale scores cannot be calculated due to missing data, the summary score will not be calculated. Figures 9.1-9.3 show the scoring sheets.
- Subjects ages 13-17 years. The Food Allergy Quality of Life Questionnaire –Teenager Form (FAQLQ-TF) for ages 13-17 years has 3 subscale scores and a summary score (<http://faqlq.com/wp-content/uploads/2011/11/FAQLQ-TF-scoring-sheet.pdf>). Subscale scores are item mean scores for completed items, and the summary score is the item mean score of all questionnaire items for completed items. If one or more subscale scores cannot be calculated due to missing data but the overall survey completeness is not lower than 80%, the summary score will be calculated. Figure 9.4 shows the scoring sheet.

Figure 9.1. FAQOL-PF scoring sheet for ages 0-3 years.

FAQoL-PF SCORING SHEET (0-3yrs)

1. Emotional Impact (EI) Subscale		2. Food Anxiety (FA) Subscale		3. Social and Dietary Limitations (SDL) Subscale	
Question	Score (0-6)	Question	Score (0-6)	Question	Score (0-6)
Input score for each question below		Input score for each question below		Input score for each question below	
Q. 2		Q. 1		Q. 3	
Q. 6		Q. 4		Q. 8	
Q. 7		Q. 5		Q. 12	
Q. 9				Q. 13	
Q. 10				Q. 14	
Q. 11					
Total		Total		Total	
Total / 6 = EI Subscale Score		Total / 3 = FA Subscale Score		Total / 5 = SDL Subscale Score	
EI Subscale Score =		FA Subscale Score =		SDL Subscale Score =	

HRQoL Summary Score = (EI Subscale Score + FA Subscale Score + SDL Subscale Score) / 3

HRQoL Summary Score = (_____ + _____ + _____) / 3 = _____

Figure 9.2. FAQOL-PF scoring sheet for ages 4-6 years.

FAQoL-PF SCORING SHEET (4-6yrs)

1. Emotional Impact (EI) Subscale		2. Food Anxiety (FA) Subscale		3. Social and Dietary Limitations (SDL) Subscale	
Question	Score (0-6)	Question	Score (0-6)	Question	Score (0-6)
Input score for each question below		Input score for each question below		Input score for each question below	
Q. 2		Q. 1		Q. 3	
Q. 6		Q. 4		Q. 8	
Q. 7		Q. 5		Q. 12	
Q. 9		Q. 16		Q. 13	

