Q. 10		Q. 17		Q. 14	
Q. 11		Q. 20		Q. 15	
Q. 23		Q. 21		Q. 18	
Q. 24				Q. 19	
Q. 25				Q. 22	
Q. 26					
Total		Total		Total	
Total / 10 = EI Subscale Score		Total / 7 = FA Subscale Score		Total / 9 = SDL Subscale Score	
EI Subscale Score =		FA Subscale Score =		SDL Subscale Score =	

HRQoL Summary Score = (EI Subscale Score + FA Subscale Score + SDL Subscale Score) / 3

HRQoL Summary Score = (_____ + _____ + _____) / 3 = _____

Figure 9.3. FAQOL-PF scoring sheet for ages 7-12 years.

FAQoL-PF SCORING SHEET (7-12yrs)					
1. Emotional Impact (EI) Subscale		2. Food Anxiety (FA) Subscale		3. Social and Dietary Limitations (SDL) Subscale	
Question	Score (0-6)	Question	Score (0-6)	Question	Score (0-6)
Input score for each question below		Input score for each question below		Input score for each question below	
Q. 2		Q. 1		Q. 3	
Q. 6		Q. 4		Q. 8	
Q. 7		Q. 5		Q. 12	
Q. 9		Q. 16		Q. 13	
Q. 10		Q. 17		Q. 14	
Q. 11		Q. 20		Q. 15	
Q. 23		Q. 21		Q. 18	
Q. 24		Q. 29		Q. 19	
Q. 25				Q. 22	
Q. 26					
Q. 27					
Q. 28					
Q. 30					
Total		Total		Total	
Total / 13 = EI Subscale Score		Total / 8 = FA Subscale Score		Total / 9 = SDL Subscale Score	
EI Subscale Score =		FA Subscale Score =		SDL Subscale Score =	

HRQoL Summary Score = (EI Subscale Score + FA Subscale Score + SDL Subscale Score) / 3

HRQoL Summary Score = (_____ + _____ + _____) / 3 = _____

Figure 9.4. FAQOL-TF scoring sheet.

FAQOL-TF SCORING SHEET (13-17 years)

Allergen avoidance & dietary restrictions (AADR)		Risk of accidental exposure (RAE)		Emotional impact (EI)	
Question	Score (range 1-7)	Question	Score (range 1-7)	Question	Score (range 1-7)
Add up the score of each question		Add up the score of each question		Add up the score of each question	
Q. 1		Q. 11		Q. 5	
Q. 2		Q. 13		Q. 12	
Q. 3		Q. 14		Q. 19	
Q. 4		Q. 15		Q. 20	
Q. 6		Q. 17		Q. 21	
Q. 7		Q. 18		Q. 22	
Q. 8				Q. 23	
Q. 9					
Q. 10					
Q. 16					
	_____ +		_____ +		_____ +
Total		Total		Total	
Total / number of completed questions=AADR domain score		Total / number of completed questions = RAE domain score		Total / number of completed questions = EI domain score	
AADR Domain Score = (_____) / (_____) = _____		RAE Domain Score = (_____) / (_____) = _____		EI Domain Score = (_____) / (_____) = _____	
Total FAQOL-TF Score = $(q1 + q2 + q3 + q4 + q5 + q6 + q7 + q8 + q9 + q10 + q11 + q12 + q13 + q14 + q15 + q16 + q17 + q18 + q19 + q20 + q21 + q22 + q23) / \text{number of completed questions}$					

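### The SAP's FAQLQ scoring keys do not fit the questionnaires printed in protocol Supplement 1, and neither document says which forms were completed

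*SAP*

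**What the plan says.** The protocol (synopsis, Section 3, and the quality-of-life paragraph of Section 6.1.2) refers families to Supplement 1 for age-specific questionnaires at enrolment and at the end of the study.

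- **Supplement 1A (Section 12.1)** is a single parent form for ages 1-12. It has 25 numbered items and one unnumbered question on OIT side effects.
- **Supplement 1B (Section 12.2)** is a form for ages 13-16 with 23 items. Item 23 asks about OIT side effects and is marked for completion only after the study.

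SAP 6.3.2 says the FAQLQ parent form "will be used for patients aged 0-12 years" and the teenager form "will be used for patients aged 13-17 year". On scoring, SAP 9.2.2 states: "Questionnaires will be scored according to scoring sheets downloaded from the FAQLQ website". It adds that the parent form "for ages 0-12 years has different scoring sheets for age group 0-3, 4-6, and 7-12", and Figures 9.1-9.3 give those three keys. The 7-12 key, for example, ends its first column with "Total / 13 = EI Subscale Score". The teen key (Figure 9.4) lists Q23 under Emotional Impact (EI) and again in the total, whose formula ends "q20 + q21 + q22 + q23".

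Two rules in SAP 9.2.2 then matter. For any score, "scores will not be calculated if the percent of missing items is greater than 20" per cent. For the parent form: "If one or more subscale scores cannot be calculated due to missing data, the summary score will not be calculated". Under SAP 10.2 only summary scores are tested, and parent and teen forms are analysed separately.

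**The concern.** A scoring key applies only to the form it was written for. Here the form is in one document and the key in another, and item counts, age bands and item content disagree. The protocol prints no age-band parent forms, and its summary of changes records no replacement questionnaire.

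If Supplement 1 was what families completed, two things follow:

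- A teen's exit score contains a rating of treatment side effects that the baseline score lacks. The trial's own hypothesis is that boiled peanut causes fewer side effects. A low rating on that item would appear as improved quality of life, so tolerability would be reported as quality-of-life change.
- Children aged 7-12 could lose the only parent-form score that is tested. They would still be counted in the parent-form analysis population, because SAP 8.2.2.2 asks for only one subscale or summary score at both visits.

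**Working it through.** **Inputs.** Item lists come from SAP Figures 9.1-9.4, and printed items from protocol Supplements 1A and 1B. The 20% rule and the parent summary rule are in SAP 9.2.2. The minimally important difference (MID) of 0.5 is in SAP 6.3.2 and 9.2.2. The 10 planned children are in protocol Section 5.

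**Step 1: are the keys consistent in themselves?** Yes. Each uses every item number once, and the parent divisors match the items listed.

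**Step 2: parent keys against Supplement 1A**, counting items not on the form as missing. FA is Food Anxiety and SDL is Social and Dietary Limitations.

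| Key | Items needed (EI+FA+SDL) | Not on 1A | EI lacking | FA lacking | SDL lacking |
|---|---|---|---|---|---|
| 0-3 | 6+3+5 = 14 | none | 0/6 | 0/3 | 0/5 |
| 4-6 | 10+7+9 = 26 | Q26 | 1/10 = 10.0% | 0/7 | 0/9 |
| 7-12 | 13+8+9 = 30 | Q26-Q30 | 4/13 = 30.8% | 1/8 = 12.5% | 0/9 |

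- *Ages 7-12:* EI exceeds 20%, so there is no EI score and no summary score. Reading the unnumbered OIT question as Q26 gives 3/13 = 23.1%, still above 20%. FA and SDL pass, so these children stay in the analysis population.
- *Ages 4-6:* all scores are calculated.
- *Ages 1-3:* all scores are calculated, but items 15-25 (11 of 25 answers) are ignored.
- *Numbering:* Supplement 1A labels two consecutive items 13 and none 12. The table reads the first as 12. Taken literally, SDL would lack 1/5 = 20.0% (0-3 key) or 1/9 = 11.1% (other keys). Neither is greater than 20%, so nothing changes.

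**Step 3: item content.** All three parent keys put Q1 and Q5 under Food Anxiety; on Supplement 1A these ask about feeling different from peers and about physical distress. The item on anxiety about food falls under SDL whether it is read as 12 or 13. For ages 4-12, Q24 and Q25 (restaurants and holidays) count as EI. Supplying the missing item numbers would not cure this.

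**Step 4: teen key against Supplement 1B.** The key has 10+6+7 = 23 items. Without Q23, baseline lacks 1/23 = 4.3% of the total and 1/7 = 14.3% of EI. Both are under 20%, so the scores are calculated and the missing-item rule gives no warning.

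Let *m* be the mean of the common items, unchanged between visits, and *x* the answer to Q23.

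- Total: (22*m* + *x*)/23 − *m* = (*x* − *m*)/23. With *m* = 4 the largest shift is 3/23 = 0.13; at the scale extremes it is 6/23 = 0.26.
- EI, with *m* now the EI mean: (6*m* + *x*)/7 − *m* = (*x* − *m*)/7. With *m* = 4 the largest shift is 3/7 = 0.43; at the extremes it is 6/7 = 0.86.

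Against the MID of 0.5, the total cannot reach it through Q23 alone. EI can, towards the extremes.

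**Step 5: what the tests can show.** The smallest exact two-sided p from a signed rank or sign test is 2/2^n: 2/32 = 0.0625 for n = 5 and 2/64 = 0.03125 for n = 6. Even if all 10 children were aged 1-12, five or more aged 7-12 would leave at most five parent summary scores, and significance at 0.05 would be impossible. The teen test likewise needs at least six teens.

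**The case against.** The strongest reply is that the published age-specific forms were probably the ones used. SAP 6.3.2 names the FAQLQ-PF and FAQLQ-TF, and SAP 8.2.2.2 requires both scores to come from the same age-group parent form, a condition with no purpose if a single form covered ages 1-12. The case report forms and mock tables are not in the text available and might settle it. In that event the keys may be right and only the supplement is wrong.

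This carries weight for the parent form, but it does not remove the contradiction. The protocol still directs families to Supplement 1, and neither document says which forms were completed. On either reading, one document needs correcting.

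Other limits stand:

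- The teen form and key agree on item count (23) and range (1-7); the only demonstrated misfit is Q23. It cannot by itself move the tested total by the MID. The larger EI shift affects a subscale that is not tested, and SAP 10.2 reports the MID percentage for summary scores only.
- The content comparison judges item wording against subscale labels, since the published forms are not reproduced in the documents.
- Lost scores would be visible, because SAP 8.4 and 9 require sample sizes and missing data to be shown.

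**Conclusion.** The concern holds. Following both documents as written gives wrong or missing FAQLQ scores, and the documents do not settle which one is in error.

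The size depends on the form used:

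- **Supplement 1B used:** teen change compares 22 items with 23, with an artefact of at most 0.26 in the total and 0.86 in EI (0.13 and 0.43 at a mid-scale mean). This assumes no other change. Unless at least six of the 10 children are teens, it mainly affects reported change scores rather than a test.
- **Supplement 1A used:** no EI or summary score for any child aged 7-12, if items never printed count as missing. The SAP does not say whether they do. If they do not, EI rests on 9 of the key's 13 items, and their content does not match the label.
- **Published forms used:** the keys may fit, and the fault is in Supplement 1.

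The age mix is not given, so the number of children affected is unknown. SAP 8.5 treats this secondary endpoint as hypothesis-generating, and the primary endpoint is untouched. It should be fixed before analysis, so that scoring choices are not made with results in view.

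**What to change.** 1. Check the completed forms and state in SAP 9.2.2 which parent and teen questionnaires were administered at each visit.
2. If the published age-specific forms were used, correct protocol Supplement 1 to show them.
3. If the Supplement 1 forms were used, replace the keys in Figures 9.1-9.4 with ones matched item by item. For Supplement 1B, drop Q23, leaving 22 items in the total and six in EI. For Supplement 1A, assign each of the 25 items to a subscale, give the basis for the assignment, and repair the duplicate number 13.
4. In either case, exclude any OIT side-effect item from all subscale, summary and change scores, and report it separately at exit.
5. State that the 20% rule applies only to items printed on the form given at that visit.

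The cost is a check of completed forms, one corrected supplement or set of keys, and a few sentences in the SAP; no new data are needed. The drawback is that, if the 25-item form was used, the parent subscales as keyed in Figures 9.1-9.3 could not be reported.

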9.2.3 Derivation of Safety Variables

Adverse events (AEs) will be categorized by preferred term using the CTCAE Version 5.0, and by the specific AEs of interest listed in section 5.2. The *specific AEs of interest* with possible alternative preferred terms, which will be grouped together, are: oral itching (oral pruritus), rhinorrhea (allergic rhinitis or rhinorrhea), conjunctivitis (eye itching), urticaria (hives), angioedema, abdominal upset (dyspepsia or nausea), vomiting, diarrhea, cough, wheeze (wheezing), and anaphylaxis.

Mortality. Mortality will be identified by an AE of CoFAR severity grade 5, and/or 'Death' indicated as a SAE criteria on the CRF for AEs.

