8.3.3 Classification of an Adverse Event

8.3.3.1 Severity of an Event

All adverse events will be graded in severity utilizing criteria specifically developed by the Consortium of Food Allergy Research.²⁷ These criteria are widely accepted and applied to OIT clinical trials.

Grade 1 Mild	Grade 2 Moderate	Grade 3 Severe	Grade 4 Life threatening	Grade 5 Death
Transient or mild discomforts (< 48 hours), no or minimal medical intervention/therapy required. These symptoms may include pruritus, swelling or rash, abdominal discomfort or other transient symptoms.	Symptoms that produce mild-to-moderate limitation in activity, some assistance may be needed; no or minimal intervention/therapy is required. Hospitalization is possible. These symptoms may include persistent hives, wheezing without dyspnea, abdominal discomfort/increased vomiting or other symptoms.	Marked limitation in activity, some assistance usually required; medical intervention/therapy required, hospitalization is possible. Symptoms may include bronchospasm with dyspnea, severe abdominal pain, throat tightness with hoarseness, and transient hypotension among others. Parenteral medication(s) are usually indicated.	Extreme limitation in activity, significant assistance required; significant medical/therapy. Intervention is required; hospitalization is probable. Symptoms may include persistent hypotension and/or hypoxia with resultant decreased level of consciousness associated with collapse and/or incontinence or other life-threatening symptoms	Death

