5.2 Endpoints

Primary Endpoints. Response to treatment defined as ability to successfully consume a single dose of 300 mg or greater of peanut protein with no dose limiting symptoms at exit double blind placebo controlled food challenge (DBPCFC).

The highest dose of roasted peanut protein tolerated by the subject at exit DBPCFC will also be compared to the highest dose tolerated at baseline.

The effect of boiled peanut immunotherapy on the immune response to peanut will be evaluated via specific serum markers of sensitization and tolerance to peanut.

- Levels of serum specific peanut IgE, with higher levels associated with greater likelihood of clinical reaction on exposure to peanut protein.

- Peanut protein component panel, to determine the presence of high levels of sensitivity to peanut proteins known to be associated with severe systemic reactions (Arah 1,2, 3) versus mild reactions (Arah8)
- Levels of peanut specific serum IgG4, with higher levels associated with increased tolerance to peanut protein

These markers will be evaluated at baseline and the conclusion of the study.

Secondary Endpoints. The rate of adverse events in the subjects receiving boiled peanut oral immunotherapy. Possible adverse events include: side effects of treatment defined as oral itching, rhinorrhea, conjunctivitis, urticaria, angioedema, abdominal upset, vomiting, diarrhea, cough, wheeze, or anaphylaxis

- Adverse events will be recorded in terms of the percentage of subjects with adverse events on initial escalation day and at dose escalation visits by CRU staff.
- Adverse events will also be recorded in terms of overall percentage of home doses that result in adverse reaction, with data compiled from home logs.

The adverse reactions will be graded in severity and the treatment required will be recorded.

Validated, age-specific, food-related quality-of-life surveys before and after peanut oral immunotherapy will be completed by all patients/families.

6 Study Methods

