11.1.1 Patient- and dose-level summary AE tables

AEs will be classified into study phases as follows: dose escalation study visits, home doses, exit

DBPCFC, and overall. Specific AEs of interest, which will be included in the patient- and dose-level AE tables whether or not any patients experienced them, are listed under Secondary Endpoints in section 5.2 and under Derivation of Safety Variables in section 9.2.3. Any additional preferred terms recorded for at least one patient or dose will also be reported, listed alphabetically following the specific AEs of interest. AEs occurring and doses of study medication administered during both arms of the exit DBPBFC will be counted towards the totals. (Refer to mock Tables 3.1 and 3.2.)

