11.1.2 Comparative AE table

AE data from this study will be compared descriptively to the AE data from three published studies: the study medication arms of the Phase 2 and Phase 3 trials of AR101 OIT for peanut allergy (Bird et al., 2018; Vickery et al. for PALISADE, 2018), and OIT data from the PACE meta-analysis study of OIT for peanut allergy (Chu et al., 2019). No hypothesis testing will be performed.

For this table, study AEs will be categorized into two study phases as best corresponds to the comparative data: 1) initial dose escalation study visit, and 2) an increasing dose phase which includes all other dose escalation study visits and home doses, but excludes the exit DBPCFC. AEs will be grouped into severity grades, treatments, and preferred terms, where the preferred term list will include the specific AEs of interest only (see sections 5.2 and 9.2.3). (Refer to mock Table 3.3 for comparative data and source information.)

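### An event coded as abdominal pain has no term row in the comparison with roasted peanut OIT, because SAP 9.2.3 maps only dyspepsia and nausea to abdominal upset

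*SAP*

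**What the plan says.** SAP 5.2 lists the adverse events of interest for the secondary endpoint: "oral itching, rhinorrhea, conjunctivitis, urticaria, angioedema, abdominal upset, vomiting, diarrhea, cough, wheeze, or anaphylaxis". Abdominal pain is not a separate item.

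SAP 9.2.3 then ties these items to coded terms, "with possible alternative preferred terms, which will be grouped together". For the abdominal item the entry is "abdominal upset (dyspepsia or nausea", with no further term before the bracket closes.

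Two reporting rules follow. For the within-study Tables 3.1 and 3.2, SAP 11.1.1 adds: "Any additional preferred terms recorded for at least one patient or dose will also be reported". For the comparative Table 3.3, SAP 11.1.2 says "AEs will be grouped into severity grades, treatments, and preferred terms", and then restricts the last of these: "where the preferred term list will include the specific AEs of interest only".

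The protocol names abdominal symptoms as reaction signs in several places. Its severity table (Protocol 8.3.3.1) gives abdominal discomfort as an example at Grades 1 and 2 and "severe abdominal pain" at Grade 3. Protocol Table 4 makes persistent severe abdominal pain a major criterion, and Protocol 6.1.2 applies Table 4 to the initial escalation day as well as to the food challenges. Protocol 7.1 lists upper abdominal pain among the symptoms that suggest eosinophilic esophagitis.

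**The concern.** Table 3.3 is the output that answers the secondary objective (SAP 5.1), a comparison of adverse effects with published roasted peanut OIT. The trial's hypothesis is that boiled peanut gives fewer of them. A symptom that the protocol uses for grading and for stopping a dosing session should be traceable by name in that comparison. Under the SAP as written it is not: the term rule leaves it out of abdominal upset, and the table rule leaves out anything that is not an event of interest.

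Two things are at stake. The table may say nothing by name about a recognised reaction. Or, if the published figures placed beside abdominal upset already include abdominal pain, the two columns would measure different things and the difference would favour boiled peanut. The SAP text states no rule for mapping the published terms, so it does not settle which of these applies.

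**Working it through.** The plan states no figure on this point, so there is none to reproduce. The check traces one event through the tables and then sizes the effect.

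**Step 1: does any event of interest take in abdominal pain?** The list in SAP 5.2 has 11 items. Apart from abdominal upset, the other ten are oral itching, rhinorrhea, conjunctivitis, urticaria, angioedema, vomiting, diarrhea, cough, wheeze and anaphylaxis. None of these covers abdominal pain as such. The alternatives given for abdominal upset in SAP 9.2.3 are dyspepsia and nausea. So an event whose preferred term is abdominal pain is mapped to no event of interest.

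**Step 2: where does that event appear?**

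| Output | Rule | Abdominal pain |
|---|---|---|
| Tables 3.1 and 3.2 (SAP 11.1.1) | Events of interest plus any other recorded term | Shown by name; no published column |
| Table 3.3, term rows (SAP 11.1.2) | Events of interest only | No row, and not counted under abdominal upset |
| Table 3.3, severity and treatment rows (SAP 11.1.2) | No restriction by term stated | Counted, but not identifiable as pain |
| Table 3.4 or 3.5 (SAP 11.1.3, 11.2.2) | All recorded terms, non-serious or serious | Shown by name; no published column |

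The gap is confined to the term rows of Table 3.3.

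**Step 3: which way could it push the comparison?**
- Published abdominal upset figures include pain: this trial's row omits events that the published row counts, so the row favours boiled peanut.
- Published figures exclude pain: the two columns match, and the table is silent on pain by name.

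The SAP refers to mock Table 3.3 for the comparative data. The mock tables are not in the text available for this review, so the choice between the two cases cannot be checked here.

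**Step 4: size.** Inputs: n = 10 patients (Protocol 9.2, SAP 7), all assumed to be in the safety population; k = number of children who, within a Table 3.3 phase, have an event coded as abdominal pain but none coded as dyspepsia or nausea.

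Reduction in the patient-level abdominal upset row = 100 × k / n percentage points.

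- k = 1: 100 × 1/10 = 10 points
- k = 2: 100 × 2/10 = 20 points
- k = 3: 100 × 3/10 = 30 points

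The range for k is an assumption. The documents give no rate of abdominal pain for this trial or for the comparator studies. A child who also has dyspepsia or nausea in the same phase is already counted, so contributes nothing to k.

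**The case against.** The strongest reply is that little is lost. Every abdominal pain event is reported by name in the within-study tables and in the registry tables. Only the term list of Table 3.3 is restricted, so a severe or treated episode still enters the comparison through the severity and treatment rows. The comparison is descriptive, so no error rate or power is affected. All of this stands, and a reader who inferred that abdominal pain vanishes from the comparison altogether would be going too far.

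A second reply is that the mapping may be looser than it looks. SAP 9.2.3 calls its terms possible alternatives, which can be read as illustrative, and mild discomfort falls within the ordinary meaning of abdominal upset. The home log (Protocol 12.3) has a combined box for nausea and upset stomach, so some home complaints may be recorded there and then grouped. This stands in part. It would lower k for home doses, but the log does not name pain, and reactions at clinic visits are recorded by staff. If the list is open, the mapping is left to judgement in a single-arm, unblinded study, which is itself a reason to settle it in advance.

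Third, a reader might infer that the plan is biased towards its own hypothesis. The documents do not show that. The term restriction may apply equally to the published columns, in which case information is lost but neither product is favoured.

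Fourth, a reader might want to express the effect as a fall in a gastrointestinal event rate, or to scale it by Protocol Table 2, where 25 of 46 adverse-event discontinuations (25/46 = 54%) were gastrointestinal. Neither is supported. No described table has a pooled gastrointestinal rate, since abdominal upset, vomiting and diarrhea are separate items. The 54% is a share of discontinuations for all gastrointestinal causes on another product, not a rate of abdominal pain.

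**Conclusion.** The point holds in a limited form. Followed literally, SAP 9.2.3 and 11.1.2 together leave an event coded as abdominal pain without a term row in the one table that compares this trial with roasted peanut OIT by symptom.

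The possible understatement is confined to the abdominal upset row: 10 points per affected child at n = 10, under the assumptions in the working. Whether it favours boiled peanut depends on how the published figures are entered, so bias is a risk and not an established result. The primary endpoint and its test are untouched. This is a modest change to a secondary-objective table, worth making before the analysis is run.

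**What to change.** Settle the mapping of abdominal pain in SAP 9.2.3 and 11.1.2 by one of two routes:

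- add abdominal pain, and abdominal discomfort if events are so coded, to the terms grouped under abdominal upset; or
- keep the grouping as it is and state in SAP 11.1.2 that Table 3.3 carries a separate abdominal pain row.

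With either route, add a sentence that the same mapping applies to the published columns wherever the sources report the term, and that a footnote will mark any source that does not.

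The cost is a few words in the SAP and one line in a mock table, with no new data or visits. The first route has a small downside: merging pain, including severe pain, with nausea makes the row less specific. The second route avoids that.
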